Clinical investigation plan

C18-652 (EX-MKTG-100)

A clinical comparison of two daily disposable soft contact lenses

**A clinical evaluation for
CooperVision Inc.**

January 2019

Contents

Document control	3
Study summary	
Section 1. Overview	6
1.1 Background	6
1.2 Personnel	6
1.3 Study objectives	6
1.4 Study design	6
1.5 Statistical considerations	6
1.6 Risk analysis	6
Section 2. Resources	8
2.1 Subject selection	8
2.2 Subject discontinuation	9
2.3 Safety parameters, adverse events and concurrent illnesses	9
2.4 Study termination	10
2.5 Protocol deviations	10
2.6 Study resources	10
2.7 Study control	11
2.8 Documentation	12
2.9 Data collection and analysis	12
2.10 Study completion	12
2.11 Confidentiality	12
2.12 Study monitoring	12
Section 3. Subject management	14
3.1 Visit scheduling	14
3.2 Visit conduct	14
3.3 Monitoring subject compliance	20
3.4 Missing, unused and spurious data	20
Section 4. Study co-ordination	21
4.1 Document processing	21
4.2 Disclosure	21
4.3 Personnel	21

Appendices

[figure not shown]

Document control

Study title: A clinical comparison of two daily disposable soft contact lenses (C18-652) (EX-MKTG-100)

[figure not shown]
Sponsor company: CooperVision Inc.

Document type:

Document author:

Document reviewed and approved by:

Document reviewed and approved by:

Study summary

This double-masked, bilateral, direct refit study will compare the clinical performance of two daily disposable contact lenses (clariti 1day and MyDay) when fitted to existing wearers of Biofinity monthly lenses.

Fifty-five subjects will be recruited and fitted with monthly Biofinity spherical lenses at the first study visit. After a month of re-useable lens wear, all subjects will be switched into daily disposable lenses (according to the randomisation table), with each study lens worn for one week.

The following will be assessed throughout the study: [REDACTED] lens fit, lens fit acceptance, first fit success [REDACTED]

[REDACTED] lens surface, [REDACTED] and subjective response [REDACTED]

A study summary is shown in Table 1.

Visit	Procedures
Information and consent presentation Visit 1: Dispensing of Biofinity	Short on-line presentation of study aims and procedures Informed consent taken Explanation of study procedures and subject instructions Ocular and contact lens history Medical history [REDACTED] Refraction [REDACTED] Fitting of Biofinity lens [REDACTED] Lens fit [REDACTED] [REDACTED]
Visit 2: One month follow-up with Biofinity, and dispensing with first daily disposable study lens	Issue study lenses, care regimen [REDACTED] Record wear times/medical/ocular history Retrieval of unused lenses, care regimen [REDACTED] Subjective scores [REDACTED] Lens fit [REDACTED] [REDACTED] Fitting of first daily disposable study lens [REDACTED] Lens fit [REDACTED] [REDACTED]
Visit 3: One week follow-up visit with first daily disposable study lens, and dispensing with second daily disposable study lens	Issue study lenses [REDACTED] Record wear times/medical/ocular history Retrieval of unused lenses [REDACTED] [REDACTED] Lens fit [REDACTED] [REDACTED] Fitting of second daily disposable study lens [REDACTED] Lens fit [REDACTED] [REDACTED]
Visit 4: One week follow-up visit with second daily disposable study lens	Issue study lenses [REDACTED] Record wear times/medical/ocular history Retrieval of unused lenses [REDACTED] [REDACTED] Lens fit [REDACTED] [REDACTED] Exit form signed [REDACTED]

Table 1: Study summary.

Section 1. Overview

1.1 Background

This project seeks to compare the clinical performance of the clariti® 1 day and MyDay® daily disposable contact lenses (CooperVision Inc.) in existing wearers of the Biofinity® monthly lens (CooperVision Inc.).

1.3 Study objectives

The aim of this clinical work is to compare the clinical performance and subjective acceptance of two daily disposable soft contact lenses (clariti 1 day and MyDay daily disposable) when a subject is switched into these from Biofinity monthly lenses.

1.4 Study design

This will be a randomised, double-masked, crossover study, in which 55 subjects who have been 'pre-conditioned' (i.e. fitted) with Biofinity spherical lenses for one month are switched into daily disposable lenses. Subjects will wear each daily disposable lens type for one week, in random order.

1.5 Statistical considerations

██████████ lens surface data and subjective responses will generate data that are likely to be continuous and normally distributed. As such, these will be compared using linear regression models or other parametric methods. Subjective preferences will be compared using chi-squared tests. Lens fit data are expected to be ordinal data and assessed with non-parametric approaches. Deviations from this statistical plan will be discussed in the final report. Deviations may be necessary due to differences between the actual data distribution compared with the anticipated data distribution.

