1.5.1 Power analysis

A power analysis for end-of-day comfort has shown that 51 subjects completing the study will provide a sufficient number of subjects for this purpose (non-inferiority testing). This will also provide enough subjects to show non-inferiority between lenses for insertion comfort and overall comfort. To allow for discontinuations, 55 subjects will be dispensed with contact lenses.

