3.2.5 Visit 4: Follow-up second daily disposable lens

This study visit will be identical to Visit 2 (Section 3.2.3) steps 1-12, with the second daily disposable lens being assessed, [REDACTED] (per 3.2.4) between Biofinity and the second daily disposable lens.

[REDACTED]

[REDACTED] the following will be carried out:

1. At the final visit (or when the subject is discontinued at an earlier visit) the subject will sign a study exit statement acknowledging that the work is complete, although they may have been asked by the investigator to attend a post-study follow-up visit, and that they should continue to use their lenses (and solutions) as advised, and seek aftercare for their contact lenses. A copy of this signed form will be issued to the subject.
2. The subject will be issued with their payment and discharged.

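### Does testing preferences with chi-squared tests ignore that each subject wears both lenses?

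*Combined protocol and SAP*

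**What the plan says.** Section 1.5 (Statistical considerations) gives preferences one sentence: "Subjective preferences will be compared using chi-squared tests". The readable text names no particular chi-squared test, table or null hypothesis, and has no rule for subjects without a preference.

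The design is in section 1.4: "This will be a randomised, double-masked, crossover study", and "Subjects will wear each daily disposable lens type for one week, in random order". Any preference information on the two daily lenses therefore comes from the same people.

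The preference questions cannot be read. Much of the subjective assessment in section 3.2.3 and part of section 3.2.4 are blacked out. Section 3.2.5 keeps a fragment about something assessed "between Biofinity and the second daily disposable lens", with a pointer to section 3.2.4, but the word saying what is assessed is hidden.

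The sample size in section 1.5.1 rests on another outcome: "A power analysis for end-of-day comfort has shown that 51 subjects completing the study will provide a sufficient number of subjects".

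**The concern.** The chi-squared test most readers think of first compares proportions between two separate groups of people. In a crossover there are no separate groups. If the plan meant that test, 51 subjects would be handled as 102 independent observations and the error rate would be wrong, in a direction set by how the table was built.

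- **Inflated.** If each subject appears once in a row for one lens and again in a row for the other, the same answer is counted twice and false positives rise.
- **Deflated.** The fragment in section 3.2.5 could mean that each daily lens is judged separately against Biofinity, giving two responses per subject. Positively correlated responses tested as independent would make the test too strict and cost power.

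Subjective acceptance is part of the aim in section 1.3, so a wrong preference test could distort a result that readers would notice.

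**Working it through.** **Inputs.** The number of completers, 51, and the number dispensed, 55, come from section 1.5.1. The two-sided 5% level (critical value 3.841 on 1 degree of freedom), the response proportions and the within-subject correlations are assumptions; the readable text gives none of them.

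**The plan's own figure.** There is no sample-size figure for preferences. The 51 is for non-inferiority on end-of-day comfort and cannot be reproduced, because level, power, margin and standard deviation are not given. From n = ((z₁₋α + z_power) × SD_diff / margin)², it implies a margin/SD_diff ratio between (1.645 + 0.842)/√51 = 0.35 (one-sided 5%, 80% power) and (1.960 + 1.282)/√51 = 0.45 (one-sided 2.5%, 90% power). The step from 51 to 55 allows for 1 − 51/55 = 7.3% discontinuation. Neither figure bears on preferences.

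**Reading 1: one preference per subject, one-sample chi-squared test.** If x of n subjects prefer one lens and n − x the other, the statistic against an even split is (2x − n)²/n. This is also McNemar's statistic, (b − c)²/(b + c), with b = x and c = n − x, so the pairing is already respected. With n = 51 it exceeds 3.841 when |2x − 51| > √(51 × 3.841) = 14.0, that is, at a split of 33 to 18 or more extreme. The exact binomial probability under the null is 0.049. If all 55 subjects answered it would be 0.058; the excess comes from the discreteness of the binomial. With 10%, 25% or 50% expressing no preference and the test run on the rest, it is 0.049, 0.049 and 0.054 (n = 51).

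**Reading 2: two yes/no responses per subject, McNemar's test.** Simulation with 400,000 runs, n = 51, response probabilities 0.5 and 0.7 and correlations from −0.3 to 0.7 gives a type I error between 0.044 and 0.053.

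**Where the alarming figures come from.**

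- *Each subject in both rows.* The table with rows (x, 51 − x) and (51 − x, x) gives 2(2x − 51)²/51, exactly twice the correct statistic. It rejects from 31 to 20 onwards. The exact type I error is 0.161; the large-sample value, P(χ²₁ > 3.841/2), is 0.166. With 50% expressing no preference it falls to 0.091.
- *Two responses tested as independent groups.* The true variance of the difference is (1 − ρ) times the assumed one, so the large-sample error is P(χ²₁ > 3.841/(1 − ρ)). Simulated values at n = 51 and probability 0.5:

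| Correlation ρ | Unpaired chi-squared | McNemar |
|---|---|---|
| −0.3 | 0.099 | 0.050 |
| 0 | 0.059 | 0.053 |
| 0.3 | 0.024 | 0.050 |
| 0.5 | 0.008 | 0.045 |

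For 70% against 50%, power would be 58% unpaired against 84% with McNemar at ρ = 0.5, and 57% against 70% at ρ = 0.3.

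**Set against the text.** Both tests in readings 1 and 2 are chi-squared tests and fit the sentence in section 1.5 as it stands. The two faulty analyses need a table that no readable section describes.

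**The case for a change.** The best argument for the concern is that the sentence does not exclude a faulty analysis. Depending on a choice that could be made after the data are seen, the same answers might be tested at a true level of about 1%, 5% or 16%. The fragment in section 3.2.5 fits a design with two responses per subject, where an unpaired comparison of the daily lenses would be a real mistake. The clause on departures from the plan does not help: it gives only one ground, "Deviations may be necessary due to differences between the actual data distribution compared with the anticipated data distribution", and says nothing of pairing. Naming the test would cost a sentence.

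Part of this stands. The form of the test, its null and the handling of subjects without a preference are not written down in the readable text, and naming them would be good practice. But allowing a misuse is different from planning one. No departure from section 1.5 is needed to run a valid test, so the narrow departure clause does no harm. The two-response design is an inference from blacked-out wording, and the unpaired clariti-versus-MyDay comparison is a second inference on top of it. Even if each daily lens is judged against Biofinity, a one-sample test of each response separately is valid. Period-adjusted tests, exact tests and a rule excluding subjects without a preference are reasonable options, but they do not correct an error.

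**Conclusion.** The concern does not hold. A chi-squared test is not by definition a test for independent groups. On the ordinary reading, one preference per subject tested against an even split, the level is 4.9% at 51 completers. If two responses per subject are compared, McNemar's test falls under the same sentence and keeps its level at 4.4% to 5.3%. The figures of 16% and 0.8% are correct arithmetic for analyses that the plan does not describe, and the second also needs an assumed correlation of 0.5.

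What remains is a small gap in detail that an analyst would fill sensibly. It concerns an outcome on which the sample size does not depend; section 1.5.1 mentions end-of-day, insertion and overall comfort, not preference. The conclusion rests on an assumed two-sided 5% level and on not reading an unpaired test into wording that is blacked out.

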1.5.1 Power analysis

A power analysis for end-of-day comfort has shown that 51 subjects completing the study will provide a sufficient number of subjects for this purpose (non-inferiority testing). This will also provide enough subjects to show non-inferiority between lenses for insertion comfort and overall comfort. To allow for discontinuations, 55 subjects will be dispensed with contact lenses.

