3.2.3 Visit 2: Follow-up with Biofinity/dispensing of first daily disposable lens

Subjects should attend wearing their Biofinity lenses which should have been in situ for at least two hours. Subjects who attend without lenses in situ for at least two hours will usually be rescheduled. The following procedures will be performed (any ocular measurement procedures outlined below will be carried out on each eye):

1. Any medical or ocular issues since the last visit will be recorded.
 2. Lens wearing times since the previous visit will be recorded (hours per day, days per week and comfortable hours per day).
 3. Lens wearing time on study visit day.
 4. Retrieval of any unused lenses (and care solution at Visit 2 only).
 5. [REDACTED]
6. The subject will be asked to score the following with reference to appropriate visual analogue scales (0-100) [REDACTED]:
- Comfort after insertion
 - Comfort before removal
 - Overall comfort
 - [REDACTED]
 - [REDACTED]

- [REDACTED]
- [REDACTED]
- [REDACTED]
- [REDACTED]
- [REDACTED]
- [REDACTED]
- [REDACTED]

7. [REDACTED]

- [REDACTED]
- [REDACTED]
- [REDACTED]
- [REDACTED]
- [REDACTED]
- [REDACTED]
- [REDACTED]
- [REDACTED]
- [REDACTED]
- [REDACTED]
- [REDACTED]
- [REDACTED]
- [REDACTED]
- [REDACTED]
- [REDACTED]

8. [REDACTED]
[REDACTED]
[REDACTED]
[REDACTED]
[REDACTED]
[REDACTED]

9. Lens fit [REDACTED] assessment, as described in section 3.2.2 (including push-up).

10. The investigator will answer the following question: “The fit of the lens is acceptable?” using the following grading scale. If the grade is 3 or more, the reasons why should be stated:

- Strongly agree
- Agree
- Neither agree not disagree
- Disagree
- Strongly disagree

11. The study lenses will be removed and discarded.
12. [REDACTED]
13. The first daily disposable study lens will be fitted and allowed to settle for five minutes, according to the randomisation table [REDACTED]
14. The same procedures as for Visit 1 (section 3.2.2) steps 8-15 will be carried out.
15. [REDACTED]
16. The subject will be discharged and asked to return for a one week follow-up visit wearing the study lenses which need to been worn for at least two hours. Subjects should be asked to wear their lenses for a minimum of eight hours per day, five days per week.

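### Non-inferiority is planned on three comfort endpoints with no testing order, adjustment or success rule; if any one may be claimed, the chance of a false claim is about 1.6 to 2.9 times the per-test level

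*Combined protocol and SAP*

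**What the plan says.** The design is a randomised two-lens crossover: "Subjects will wear each daily disposable lens type for one week, in random order" (section 1.4).

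Section 1.5.1 gives the sample size: "A power analysis for end-of-day comfort has shown that 51 subjects completing the study will provide a sufficient number of subjects for this purpose", the purpose being non-inferiority testing. It continues: "This will also provide enough subjects to show non-inferiority between lenses for insertion comfort and overall comfort". It then adds: "To allow for discontinuations, 55 subjects will be dispensed with contact lenses".

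Section 1.5 gives the analysis of subjective responses only in general terms: "these will be compared using linear regression models or other parametric methods". Neither section states a significance level, sidedness, margin, testing order, adjustment or success rule in its readable text, and no endpoint is called primary.

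The follow-up scores are listed in section 3.2.3, step 6, on 0-100 visual analogue scales. They include "Comfort after insertion", a comfort score before removal and an overall comfort score. A separate score, labelled only Comfort, is taken at fitting after five minutes' settling (section 3.2.2, steps 7 and 10). It is repeated for the first daily disposable under section 3.2.3, step 14 ("The same procedures as for Visit 1 (section 3.2.2) steps 8-15 will be carried out") and for the second under section 3.2.4.

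**The concern.** Section 1.5.1 speaks of showing non-inferiority on three endpoints from the same subjects. That is the language of a conclusion, not of description. Three tests at an unadjusted level, with success on any one reported as non-inferiority, carry a higher chance of a false conclusion than the single test on which the 51 was based. Nothing in the plan prevents a claim on insertion or overall comfort if end-of-day comfort fails. The credibility of whichever comfort claim is made is at stake; the conduct of the trial is not.

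**Working it through.** **Inputs from the protocol.** Three endpoints, 51 completers and 55 dispensed (section 1.5.1); a two-lens crossover, so paired differences (section 1.4).

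**Assumptions, because the protocol gives no value.** One-sided level α of 2.5% or 5% per test; equal correlation ρ between the three test statistics, from 0 to 0.9; all three true differences exactly at the margin; no adjustment; success means at least one test passes.

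**The plan's own figure.** The 51 cannot be reproduced without a margin, standard deviation, level and power. It can be inverted. For a paired non-inferiority test with true difference zero, margin / SD of the difference = (z(1-α) + z(power)) / √51, with √51 = 7.141:

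- α 5%, power 80%: (1.645 + 0.842) / 7.141 = 0.35
- α 2.5%, power 80%: (1.960 + 0.842) / 7.141 = 0.39
- α 5%, power 90%: (1.645 + 1.282) / 7.141 = 0.41
- α 2.5%, power 90%: (1.960 + 1.282) / 7.141 = 0.45

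The step from 51 to 55 is coherent: it implies a loss of 4/55 = 7.3%, and 51 / (1 - 4/55) = 55. These checks show that 51 fits a single test at conventional settings. They do not show which settings were used.

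**False-claim rate, independent tests.** 1 - (1 - α)³:

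- 1 - 0.975³ = 7.3%, which is 2.93 times 2.5%
- 1 - 0.95³ = 14.3%, which is 2.85 times 5%

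**False-claim rate, correlated tests.** With c = z(1-α), the rate is 1 - ∫ φ(u) · Φ((c - √ρ·u) / √(1-ρ))³ du, by numerical integration:

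| ρ | α = 2.5% | ratio | α = 5% | ratio |
|---|---|---|---|---|
| 0 | 7.3% | 2.93 | 14.3% | 2.85 |
| 0.5 | 6.3% | 2.51 | 11.8% | 2.37 |
| 0.7 | 5.5% | 2.18 | 10.3% | 2.05 |
| 0.8 | 4.9% | 1.96 | 9.3% | 1.85 |
| 0.9 | 4.2% | 1.67 | 8.0% | 1.59 |

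The ratio falls below 2 once ρ exceeds about 0.79 (α 2.5%) or 0.73 (α 5%).

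**Fewer endpoints at the margin.** With two at the margin, the rate from those two is 4.9% to 3.5% at α 2.5%, and 9.8% to 6.8% at α 5%, for ρ from 0 to 0.9. With one at the margin it is α. The table is therefore the unfavourable case.

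**After a fixed order.** A false claim requires the first endpoint in the sequence that is truly at the margin to pass, and that has probability at most α. The ratio returns to 1.0.

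**The alternative of splitting the level.** Bonferroni over three tests needs 51 × [(z(1-α/3) + z(power)) / (z(1-α) + z(power))]² completers. At α 2.5% this is 69 (80% power) or 66 (90%); at α 5% it is 73 or 70. This takes 51 as correctly sized for one test.

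**The case against.** **Section 1.5.1 is a sample-size statement, not a claims rule.** This is the strongest objection, and it stands in part. End-of-day comfort is the only endpoint with its own power analysis and can fairly be read as primary. If all three had to pass, there would be no inflation. A reader might infer that the protocol allows a claim on any one endpoint; it does not say so, and the figures above depend on that condition. But it does not say the opposite either. If end-of-day comfort is taken as a gate and is truly non-inferior, the other two endpoints still have no order between them, and the two-endpoint figures apply as an upper guide.

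**High correlation.** The three follow-up scores come from the same subject, lens, visit and scale, and one is an overall rating. Correlation of 0.8 or 0.9 is plausible, so a flat statement that the error is two to three times the per-test level is not supported. The range must include ratios below 2.

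**Insertion comfort and a fourth test.** A reader might infer that insertion comfort could equally mean the five-minute fitting score, which would add a fourth test (9.6% at α 2.5% if independent). The documents do not support giving this weight. The three follow-up labels in section 3.2.3, step 6, match the three endpoints of section 1.5.1 one for one, and the fitting score is labelled only Comfort. The mapping is worth stating, but it plays no part in the figures.

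**Joint power.** A reader might also infer that 51 is too few because the chance of passing all three is only 0.8³ = 51% for independent endpoints at 80% power each. Section 1.5.1 claims no joint power, and no per-endpoint power is given, so that criticism does not hold.

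**Redaction.** Section 1.5 and the visit procedures carry redactions, which limits what can be called absent. Section 1.5.1 shows none, and the mark in section 1.5 sits in a list of variables, so this weakens the point only modestly.

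**Conclusion.** The point holds as a gap in the plan: non-inferiority is intended on three comfort endpoints, and the readable text has no order, adjustment or success rule. Its size is conditional. The chance of at least one false claim is about 4.2% to 7.3% at one-sided 2.5% per test, or 8.0% to 14.3% at one-sided 5%. This requires that any one endpoint may be claimed without adjustment and that all three true differences lie at the margin, with correlation between 0.9 and 0. It does not show that the protocol commits to such a rule, or that 51 completers are too few. It should be corrected because it bears on which claims can be believed, but it does not invalidate the trial.

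**What to change.** State in section 1.5.1 that end-of-day comfort, defined as the one-week Comfort before removal score, is the primary non-inferiority test at the full level. The one-week scores for comfort after insertion and overall comfort are then tested in a pre-stated fixed order, stopping at the first failure. Any endpoint after a failure is reported descriptively. The order of the last two is the sponsor's choice, provided it is written down before the data are seen. The level and its sidedness should appear in the same place, since otherwise the full level is undefined.

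The cost is a few sentences. No extra subjects are needed, against roughly 66 to 73 completers under Bonferroni, and end-of-day comfort loses no power. The downside is that a later endpoint cannot be claimed after an earlier failure, however favourable its own result.
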